8.2 Endpoints

The primary endpoint is the frequency of DLTs that are classified as either possibly, probably, or definitely related to study treatment according to NCI Common Terminology Criteria for Adverse Events (CTCAE v5.0). DLTs are specified in section 4.5.2. Adverse events and DLTs will be compiled separately for each phase I cohort (triple and quadruple therapy). Any patient receiving at least one dose any of study drug will be evaluable for toxicity.

Secondary endpoints include the clinical response rates in the phase II cohorts by RECIST criteria with a lower one sided 80% confidence interval. The clinical benefit rate (rate of complete response, partial response or stable disease) will also be computed with a lower one-sided confidence bound for the symptomatic brain metastasis group. Both clinical response and clinical benefit rates will apply to evaluable patients defined as having completed 4 weeks of therapy.

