5.3.2.2 Secondary Endpoints – Efficacy

Secondary efficacy endpoints of the study include PFS and ORR in all randomized participants.

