8.1 Objectives

Primary Objective

- To nominate a recommended phase II regimen (RP2R) of triple or quadruple therapy with encorafenib +/- binimetinib + nivolumab and + ipilimumab in *BRAF* mutated, metastatic melanoma.

Secondary Objectives

- To estimate the RECIST response rate of triple or quadruple therapy in high risk populations of *BRAF* mutated, metastatic melanoma.
- To estimate the CNS clinical benefit rate (CBR, defined as complete response [CR] + partial response [PR] + stable disease [SD] >6 months) per RANO-MB criteria of triple or quadruple therapy in *BRAF* mutated, metastatic melanoma to the CNS
- To describe the toxicity, by CTCAEv5, of triple or quadruple therapy in *BRAF* mutated, metastatic melanoma
- To summarize the progression-free survival of triple or quadruple therapy in high risk populations of *BRAF* mutated, metastatic melanoma

Exploratory Objectives

6. To evaluate association between treatment response and baseline tumor mutational burden, changes in the tumor microenvironment (IFN associated gene expression), T cell clonality, and other biospecimens before and after triple or quadruple therapy.

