5-6	4	18-19	12
7	5	20-21	13
8-9	6	22	14
12	8	23-24	15
13-14	9	25-26	16
15-16	10		

For example, if 6 DLTs are observed among the first 9 patients the stopping rule for 60% DLT is enacted to signal trial suspension. The accumulated toxicities will then be evaluated by the Data and Safety Monitoring Committee for further action.

Inference from a complete 30 patient expansion cohort.

If either of the expansion cohorts runs to completion without stopping due to excess toxicity, confidence intervals can be used for inference. First, to rule out excess toxicity, an upper 90% one-sided confidence intervals (table 8.3) provides an upper bound to the DLT rate (analogous to the phase I approach). Secondly, a lower 80% one-sided confidence bound (table 8.4) can be used to rule out an ineffective regimen. (A narrower, 80% bound is used here since we want a decision that is only suggestive rather than definitive).

Table 8.3 Upper Confidence Bounds for DLT Rate

Table 8.4 Lower Confidence Bounds for Response

Number of DLTs Among 30 Treated	Upper Bound of 90% Confidence Interval (%)
0	7%
1	12%
2	17%
3	21%
4	25%
5	29%
6	32%
7	36%
8	40%
9	43%

10	46%
11	50%
12	53%
13	57%
14	60%
15	63%

Operating characteristics of possible decision rules in phase II

If a 30-patient phase II cohort is completed the following decisions are possible:

If 23 or more DLTs are observed among 30 patients the combination can be considered as too toxic and a DLT rate of 75% or greater cannot be ruled out. The probability of 23 or more DLTs with a 75% DLT rate is 92%. If the actual rate is 40% or less, the probability of 14 or fewer DLTs is 82%

Number of Responses Among 30 Treated	Lower Bound of 80% Confidence Interval (%)
0	0%
1	0%
2	3%
3	5%
4	8%
5	10%
6	13%
7	16%
8	19%
9	22%
10	25%
11	28%
12	31%

Considering a preliminary assessment of efficacy, three or fewer objective responses will suggest lack of efficacy with a response rate no better than 5%. The probability of observing 3 or fewer responses when the actual rate is 5% is 94%. However, if the actual response rate is 20% the probability of 4 or more responses is 87%.

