8.4 Proposed Analysis of Primary and Secondary Endpoints

Based on NCI Common Terminology Criteria for Adverse Events (CTCAE v5.0), the term toxicity is defined as AEs that are classified as either possibly, probably, or definitely related to study treatment. The maximum grade for each type of toxicity will be recorded for each patient, and frequency tables will be reviewed to determine toxicity patterns. The number of occurrences of each event will be tabulated by event and grade. In addition, the total number of patients experiencing AEs over their course of treatment will be characterized by type of AE and grade. For this summary grades will be grouped into Grade I/II vs III/IV. In addition, the number of patients experiencing a dose-limiting toxicity as defined in table 4.5.2 will be compiled. Inferences regarding recommended phase II regimen and safety in both phase I and phase II cohorts will be made by calculating the proportion of patients with a dose-limiting toxicity with a one sided upper 90% confidence bound.

For the phase II cohorts, both the objective response rate (complete or partial response) / total evaluable) and the clinical benefit rate (complete or partial response + stable disease / total evaluable) will be computed with lower 80% confidence bounds. Evaluable patients are those who got at least one dose of ipi/nivo. Progression-free survival will be estimated with 90% two-sided confidence intervals for each phase II cohort. For progression-free survival, an event is defined as disease-progression or death.

For exploratory biomarker analyses, Spearman's correlation will be used for continuous variables such as Ki67+, T cell-inflamed GEP, pathway enrichment scores, TMB and others. Wilcoxon rank-sum test will be used to compare TMB between groups. Fisher's exact test will be used to compare the fraction of mutated and non-mutated samples per gene and R vs NR between T cell-inflamed and non-inflamed groups. Recognizing RNAseq values are relative, we created a frozen reference set from TCGA using our previous work and bring newly collected samples to the same baseline by comparing to this reference. We transform new data into the reference set using linear regression and determining per sample T cell-inflamed score (>8.24; T cell-inflamed, <6.43; non-T cell-inflamed and others intermediate). Benjamini-Hochberg procedure will be used to control FDR from multiple comparisons. All tests will be two-sided.

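### Sections 8.2 and 8.4 define the evaluable patients for ORR and CBR differently, and both CBR formulas drop the 6-month minimum that the objective sets for stable disease

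*Combined protocol and SAP*

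**What the plan says.** **Who is counted.** Section 8.2: "Both clinical response and clinical benefit rates will apply to evaluable patients defined as having completed 4 weeks of therapy". Section 8.4, for the same two rates: "Evaluable patients are those who got at least one dose of ipi/nivo". Section 5.3.2.2 adds: "Secondary efficacy endpoints of the study include PFS and ORR in all randomized participants". The design in 3.1 is open label with enrolment by cohort; no randomisation is described anywhere.

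**What the operating characteristics assume.** Table 8.4 in section 8.3 is headed "Number of Responses Among 30 Treated". The text beside it says that "three or fewer objective responses will suggest lack of efficacy with a response rate no better than 5" per cent. It gives a 94% probability of 3 or fewer responses at a true rate of 5%, and 87% for 4 or more at a true rate of 20%.

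**What counts as clinical benefit.** The objective (synopsis, 1.3 and 8.1) is a CNS rate by RANO criteria, "defined as complete response [CR] + partial response [PR] + stable disease [SD] >6 months". Section 8.2 writes "The clinical benefit rate (rate of complete response, partial response or stable disease") and limits it to the symptomatic brain metastasis group. Section 8.4 writes "the clinical benefit rate (complete or partial response + stable disease / total evaluable") and applies it to the Phase II cohorts, with no mention of CNS disease or RANO.

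**The concern.** One word, evaluable, carries two meanings for the same endpoints. If any dosed patient fails to complete 4 weeks, two analysts who each follow a stated rule will report different rates and different lower bounds from the same data. In an open-label study with investigator-assessed response, that leaves the choice of denominator open after the results are known.

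The two sets are also not equally sound. Completing 4 weeks is a post-treatment event, reached eight weeks before the first scheduled response scan (section 5.3). Early loss is plausible: the population is high risk, and the synopsis anticipates DLTs in up to 30–50% of patients within a 6-week window. Patients lost to early death or progression are unlikely responders, so leaving them out tends to flatter the regimen.

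The CBR wording pulls the same way. Without a minimum duration, stable disease at a single week-12 scan counts as benefit under 8.2 and 8.4 but not under the objective.

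**Working it through.** **1. Reproduce the plan's figures at n = 30.** The exact one-sided lower 80% bound for x responses in n is the 0.20 quantile of a Beta(x, n − x + 1) distribution.

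- 3/30 gives 5.2%, 6/30 gives 13.3%, 9/30 gives 22.1% and 12/30 gives 31.3%. Table 8.4 prints 5%, 13%, 22% and 31%.
- Binomial: P(X ≤ 3 | 30, 0.05) = 93.9% (printed 94%); P(X ≥ 4 | 30, 0.20) = 87.7% (printed 87%).

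The printed figures are therefore right for a denominator of 30. The table heading refers to treated patients, which fits the 8.4 set.

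**2. Change the denominator.** The documents give no rate of stopping before week 4, so the numbers removed are assumptions. Take 6 responders among 30 dosed patients and remove only non-responders, as 8.2 would if early losses do not respond:

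| Removed under 8.2 | Evaluable | ORR | Lower 80% bound |
|---|---|---|---|
| 0 | 30 | 6/30 = 20.0% | 13.3% |
| 3 | 27 | 6/27 = 22.2% | 14.8% |
| 6 | 24 | 6/24 = 25.0% | 16.7% |

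Removing six such patients adds 25.0 − 20.0 = 5.0 percentage points to the rate and 16.7 − 13.3 = 3.4 to the bound, with no change in what the treatment did.

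**3. Compare the CBR definitions.**

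- Objective: CR + PR + stable disease lasting more than 6 months, in CNS disease, by RANO.
- 8.2: CR + PR + stable disease, no duration, symptomatic brain metastasis group.
- 8.4: CR + PR + stable disease, no duration, the Phase II cohorts.

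Within a given set of patients, everyone who meets the objective's definition also meets the formulas in 8.2 and 8.4, but not the reverse. The rate as written is therefore at or above the rate as defined. The gap is the share of patients whose best outcome is stable disease of 6 months or less, which the documents do not give. Purely as illustration, with 9 responders and 6 patients with stable disease among 30, CBR is 15/30 = 50.0% if all six count, 12/30 = 40.0% if three last long enough, and 9/30 = 30.0% if none do.

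**The case against.** **The third population.** A reader might infer three competing analysis sets for ORR. The documents do not support that. With no randomisation, the phrase in 5.3.2.2 defines no set that an analyst could use; it is a wording error. The working conflict is between 8.2 and 8.4.

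**The 94% and 87%.** A reader might infer that these are wrong. They are not: they are conditioned on a completed 30-patient cohort and reproduce at n = 30. Section 8.3 also says that 30 patients will be evaluated for response and benefit in each cohort, which can be read as 30 evaluable patients under 8.2 as well.

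**Loss of power.** It is tempting to add that the chance of 4 or more responses at a true 20% falls to 81.8% with 27 evaluable patients or 73.6% with 24. Those figures need the removed patients to respond as often as the rest, in which case ORR is not biased upward. If the removed patients never respond, the responder count is unchanged and the probability stays at 87.7%. The two harms rest on opposite assumptions and should not be claimed together. Likewise, moving from 4 responses to 3 under the response rule requires a patient who stops before week 4 and is still scored a responder; this is possible, since follow-up continues after treatment stops (3.6), but it is not the likely case.

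**Shorthand.** The CBR wording in 8.2 and 8.4 may simply abbreviate a term defined in 8.1, and Appendix 5.8a refers to minimum criteria for the duration of stable disease. But the appendix gives no number, and sections 1.1.3.1 and 8.2 both spell out clinical benefit without a duration, so the abbreviation cannot be taken for granted.

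What stands after this: the 8.2/8.4 conflict, the likely direction of the bias, and the missing duration and CNS restriction in the CBR formulas.

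**Conclusion.** The plan is inconsistent on two points and should be corrected. First, 8.2 and 8.4 define evaluable patients differently for the same ORR and CBR, and the 8.2 definition selects on an event after treatment starts. In the worked case the reported ORR rises from 20.0% to 22.2% or 25.0%, assuming that 3 or 6 of 30 dosed patients are removed and that none of them responds. The upward direction is likely rather than certain: it depends on early losses responding less often than the patients kept. Second, the CBR formulas omit the 6-month condition, and 8.4 also omits the restriction to CNS disease by RANO. The missing duration can only hold the rate level or raise it, by an amount that the documents do not allow one to calculate.

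The consequence is limited. These are secondary endpoints, section 8.3 describes the 80% bound as suggestive rather than definitive, and neither the choice of Phase II regimen nor any safety rule depends on them. No printed sample-size or probability figure for response is shown to be wrong by this point.

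**What to change.** - **8.2:** delete the 4-week sentence.
- **8.2 and 8.4, denominator:** use patients with at least one dose of ipi/nivo. For ORR, apply this in each Phase II cohort. For CBR, apply it in the symptomatic brain metastasis group (Group 1) only, assessed by RANO-BM. Using all Phase II patients for CBR would put Group 2, who need not have brain lesions, into a CNS rate.
- **Missing assessments:** count patients with no post-baseline assessment as non-responders. Keep 4-week completers at most as a sensitivity analysis.
- **5.3.2.2:** refer to all treated participants in place of randomised ones, for both PFS and ORR.
- **8.2 and 8.4, CBR formula:** write CR + PR + SD >6 months, with the duration of stable disease measured from the start of treatment as in Appendix 5.10a. Because scans are 12 weeks apart, it would help to say which scan establishes that 6 months has been exceeded.

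The cost is wording in three sections, with no extra patients or scans. The downside for the sponsor is that the reported ORR and CBR will probably be slightly less favourable.

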8.3 Sample Size Considerations

Twelve patients will be evaluated in each phase I cohort; 30 patients will be evaluated for clinical response and clinical benefit in each phase II cohort. The total enrollment, in the absence of early stopping, is 84 patients (24 phase I / 60 phase II). Inference regarding safety of each cohort will depend upon the proportion of patients with DLT. An upper 90% confidence bound on these estimates can be used as a “rule out” criteria by the investigator such that any an unacceptably high DLT rate that is greater than the upper confidence interval may be ruled out.

Table 8.1 Upper Confidence Bounds for DLT Rate

Number of DLTs Among 12 Treated	Upper Bound of 90% Confidence Interval (%)
0	17
1	29
2	39
3	48
4	56
5	64
6	71
7	78
8	85
9	90
10	95
11	99
12	100

For example (see table 8.1), if none of 12 patients have a DLT one could claim the DLT rate is no higher than 17%, If 6 of 12 patients have treatment-related DLT the upper confidence bound is 71%, that is, the observed data (6/12) is consistent with a rate up to but not higher 71% . thus, one can rule out a DLT rate of 72% or greater.

Phase II cohorts will be used to (1) further refine the safety profile by re-estimating the DLT rate and (2) providing a preliminary estimate of efficacy.

While the phase II cohorts are accruing, The DLT rate will be continuously monitored and the trial will be suspended if the DLT rate appears to be too high. We assume, a priori, the DLT rate is thought to be 50%. A continuous monitoring program will be implemented to

detect if this assumption is an underestimate such that the rate were actually 60% or higher. Beginning with the 5th patient, continuous Bayesian monitoring calculates the probability that the DLT rate is too high and provides a stopping rule. We assume a prior

DLT probability of 50% and that the prior probability has a beta distribution with parameters 1.5 and 1.5, producing a mean of .5. As each evaluable patient is evaluated for DLT, accumulated data is used to derive the posterior probability. If the posterior probability of a DLT rate of 60% is 50% or greater, the stopping rule in the table is triggered.

The following tables provides rules for suspending the trial if the actual rate is as high as 60%:

Table 8.2 DLTs Triggering Trial Suspension at 60%

Number of Evaluable Patients (Inclusive)	Suspend if there are This many DLTs	Number of Evaluable Patients (Inclusive)	Suspend if there are This many DLTs
0-4	-----	17	11
5-6	4	18-19	12
7	5	20-21	13
8-9	6	22	14
12	8	23-24	15
13-14	9	25-26	16
15-16	10		

For example, if 6 DLTs are observed among the first 9 patients the stopping rule for 60% DLT is enacted to signal trial suspension. The accumulated toxicities will then be evaluated by the Data and Safety Monitoring Committee for further action.

Inference from a complete 30 patient expansion cohort.

If either of the expansion cohorts runs to completion without stopping due to excess toxicity, confidence intervals can be used for inference. First, to rule out excess toxicity, an upper 90% one-sided confidence intervals (table 8.3) provides an upper bound to the DLT rate (analogous to the phase I approach). Secondly, a lower 80% one-sided confidence bound (table 8.4) can be used to rule out an ineffective regimen. (A narrower, 80% bound is used here since we want a decision that is only suggestive rather than definitive).

Table 8.3 Upper Confidence Bounds for DLT Rate

Table 8.4 Lower Confidence Bounds for Response

Number of DLTs Among 30 Treated	Upper Bound of 90% Confidence Interval (%)
0	7%
1	12%
2	17%
3	21%
4	25%
5	29%
6	32%
7	36%
8	40%
9	43%

10	46%
11	50%
12	53%
13	57%
14	60%
15	63%

Operating characteristics of possible decision rules in phase II

If a 30-patient phase II cohort is completed the following decisions are possible:

If 23 or more DLTs are observed among 30 patients the combination can be considered as too toxic and a DLT rate of 75% or greater cannot be ruled out. The probability of 23 or more DLTs with a 75% DLT rate is 92%. If the actual rate is 40% or less, the probability of 14 or fewer DLTs is 82%

Number of Responses Among 30 Treated	Lower Bound of 80% Confidence Interval (%)
0	0%
1	0%
2	3%
3	5%
4	8%
5	10%
6	13%
7	16%
8	19%
9	22%
10	25%
11	28%
12	31%

Considering a preliminary assessment of efficacy, three or fewer objective responses will suggest lack of efficacy with a response rate no better than 5%. The probability of observing 3 or fewer responses when the actual rate is 5% is 94%. However, if the actual response rate is 20% the probability of 4 or more responses is 87%.

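### Table 8.2 leaves out the suspension boundaries at 10-11 and beyond 26 evaluable patients; under continuous monitoring the omission has an effect only at 11 and 29 patients, and the effect is small.

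*Combined protocol and SAP*

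**What the plan says.** Section 8.3 sets out a Bayesian rule for suspending phase II on DLTs.

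- **Timing.** "Beginning with the 5th patient, continuous Bayesian monitoring calculates the probability that the DLT rate is too high and provides a stopping rule". The update is made patient by patient: "As each evaluable patient is evaluated for DLT, accumulated data is used to derive the posterior probability".
- **Prior.** The section assumes a prior "DLT probability of 50% and that the prior probability has a beta distribution with parameters 1.5 and 1.5, producing a mean of .5".
- **Trigger.** "If the posterior probability of a DLT rate of 60% is 50% or greater, the stopping rule in the table is triggered".
- **Size.** "30 patients will be evaluated for clinical response and clinical benefit in each phase II cohort". Once a cohort is complete, inference passes to confidence bounds: "If either of the expansion cohorts runs to completion without stopping due to excess toxicity", Table 8.3 applies.
- **Worked example.** "if 6 DLTs are observed among the first 9 patients the stopping rule for 60% DLT is enacted to signal trial suspension".

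Table 8.2 lists evaluable patients and DLTs as follows: 5-6: 4; 7: 5; 8-9: 6; 12: 8; 13-14: 9; 15-16: 10; 17: 11; 18-19: 12; 20-21: 13; 22: 14; 23-24: 15; 25-26: 16. It has no entry for 10, 11, 27, 28, 29 or 30.

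The synopsis prints a second suspension table. That one is unbroken from 5 to 29 patients and has different values, for example 9 DLTs at 10-11.

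**The concern.** The text promises a check after every evaluable patient and makes the table the instrument that triggers suspension. At six counts within a 30-patient cohort the table is silent. Someone applying it as printed would see no signal at a count where the plan's own posterior criterion is met.

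The clearest case is 7 DLTs in 11 patients. The criterion is met, the table shows nothing, and if patient 12 has no DLT then 7 of 12 lies below the printed boundary of 8. The signal is passed over and accrual continues. This is the operating safety rule for a combination whose DLT rate is assumed in advance to be 50%.

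**Working it through.** **Inputs (Section 8.3).** Prior Beta(1.5, 1.5); threshold 60%; posterior cut-off 50%; monitoring from patient 5 after each evaluable patient; 30 patients per cohort. The posterior probability of a 60% rate is read as P(rate > 0.60).

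**Step 1: reproduce the printed table.** After k DLTs in n patients the posterior is Beta(1.5 + k, 1.5 + n − k). The boundary b(n) is the smallest k with P(rate > 0.60) ≥ 0.50. This matches all 20 printed patient counts. The plan's example of 6 in 9 gives Beta(7.5, 4.5) and P = 0.589. Cut-offs of 0.6, 0.7 and 0.8 match only 11, 2 and 0 of the 20. A rule based on a posterior mean of at least 0.60 gives the same boundaries, so the result does not depend on how the trigger sentence is read.

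**Step 2: fill in the missing counts with the same rule.**

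| n | b(n) | P at b(n) | P with one DLT fewer |
|---|---|---|---|
| 10 | 7 | 0.674 | 0.446 |
| 11 | 7 | 0.537 | 0.321 |
| 27 | 17 | 0.585 | 0.435 |
| 28 | 18 | 0.641 | 0.495 |
| 29 | 18 | 0.553 | 0.409 |
| 30 | 19 | 0.609 | 0.466 |

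A boundary exists at every count, so these are omissions.

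**Step 3: find where the omission can matter.** A cohort still running after n − 1 patients has at most b(n − 1) − 1 DLTs, and one more patient brings it to at most b(n − 1). It can therefore first cross at n only if b(n) = b(n − 1).

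- n = 10: 7 against 6 at n = 9, so no. Seven in 10 implies at least 6 in 9, which the printed table already stops.
- n = 11: 7 against 7, so yes.
- n = 27: 17 against 16, so no.
- n = 28: 18 against 17, so no.
- n = 29: 18 against 18, so yes.
- n = 30: 19 against 18, so no.

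**Step 4: size.** An exact binomial recursion over one 30-patient cohort gives the probability of suspension:

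| True DLT rate | Completed table | Printed table |
|---|---|---|
| 50% | 48.8% | 47.5% |
| 60% | 78.2% | 76.7% |
| 70% | 95.8% | 95.1% |
| 75% | 98.9% | 98.6% |

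At a true 60% rate, 5.37% of cohorts first cross at n = 11 and 0.83% at n = 29. The net loss is smaller than their sum because most cohorts at 7 in 11 are suspended later:

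- 0.60 × 5.37% = 3.22% have a DLT in the next patient and stop at 8 in 12, one patient late.
- Starting from 7 in 11, 88.4% are suspended at some later point under the printed table and 11.6% never are. On average 4.3 further patients are evaluated.
- Net loss = 0.116 × 5.37% + 0.83% = 0.62% + 0.83% = 1.45 percentage points, which is the gap between 78.15% and 76.70%.

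Expected patients before suspension or completion rise from 13.0 to 13.3.

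**Step 5: check whether the synopsis table fills the gap.** The same prior and cut-off with a 75% threshold reproduce all 25 of its counts (5 to 29). It applies a different criterion, so its 9 at 10-11 cannot stand in for the 7 that the 60% rule gives.

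**The case against.** The strongest reply is that the criterion itself is complete. Prior, threshold, cut-off and update schedule are all stated, and a statistician can derive the missing rows in minutes. Section 7 also lets the monitoring committees suspend accrual on what they review. This stands in part: what is incomplete is the tabulation. But Section 8.3 names the table as the thing that triggers suspension, and a table is what people apply.

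A second reply is that the rows may have been lost in converting the PDF. The layout argues against it. The right-hand column runs from 17 to 26 without a break beside the gap, so a lost full row would have taken an entry there too, and the last right-hand cell is empty.

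A third reply stands in full. If the synopsis table governs, the gaps in Table 8.2 no longer matter. The documents do not say which table governs.

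A reader might also infer more than the plan supports: that monitoring fails throughout 10-11 and for the last four patients, or that 7 DLTs in 10 would go unnoticed. Step 3 shows otherwise. Four of the six missing counts cannot be a first crossing, 7 in 10 is already caught at 6 in 9, and a signal at the 30th patient stops no further accrual in a 30-patient cohort.

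**Conclusion.** Wrong as written, minor in size. Table 8.2 does not deliver the continuous rule that Section 8.3 describes, and at 7 DLTs in 11 patients or 18 in 29 it is silent where the plan's own criterion calls for suspension. The loss in suspension probability is about 1.5 percentage points at a true 60% rate and no more than that at the other rates checked. It does not undermine the monitoring plan as a whole.

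The figures rest on three assumptions.

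- **DLTs are counted per 30-patient cohort.** The text does not say whether they are pooled. If they are pooled across phase II, the untabulated range runs from 27 up to 60 patients and the percentages above do not apply.
- **Outcomes are assessed one patient at a time.** If several are reviewed together, a missing count such as 10 could be the first one examined.
- **Table 8.2 is the governing table.**

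**What to change.** 1. Complete Table 8.2 from the plan's own prior and cut-off: 10-11: 7; 27: 17; 28-29: 18. Add 30: 19 for completeness, and extend further if a cohort can exceed 30 (the synopsis gives Group 2 the remainder of 60) or if DLTs are pooled. Alternatively, add one sentence saying that the posterior criterion governs at every evaluable count from the 5th patient on and that the table is only an aid.
2. Say whether DLTs are counted per cohort or across both.
3. Reconcile Table 8.2 with the synopsis suspension table and state which one governs. Settle this first, because the rows in item 1 apply only if the 60% rule stands.

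Item 1 costs a few table rows or one sentence. Items 2 and 3 need a decision by the investigators and the statistician and a text amendment. None of the three changes the sample size or the data collected.

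### The Phase II operating characteristics in Section 8.3 do not describe the monitored design: under Table 8.2 an unsuspended cohort cannot reach 23 of 30 DLTs, and the synopsis suspension table gives different properties again

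*Combined protocol and SAP*

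**What the plan says.** Section 8.3 plans 30 patients per Phase II cohort: "30 patients will be evaluated for clinical response and clinical benefit in each phase II cohort". The working assumption is "We assume, a priori, the DLT rate is thought to be 50" per cent. Monitoring is patient by patient: "Beginning with the 5th patient, continuous Bayesian monitoring calculates the probability that the DLT rate is too high and provides a stopping rule". The prior is stated ("the prior probability has a beta distribution with parameters 1.5 and 1.5, producing a mean of .5"), and so is the trigger: "If the posterior probability of a DLT rate of 60% is 50% or greater, the stopping rule in the table is triggered". Table 8.2 lists the resulting counts, with a worked example: "For example, if 6 DLTs are observed among the first 9 patients the stopping rule for 60% DLT is enacted to signal trial suspension". A trigger sends the data to the Data and Safety Monitoring Committee; it does not end the trial automatically.

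For a cohort that finishes without being stopped for toxicity, the section then gives decision rules. One is "If 23 or more DLTs are observed among 30 patients the combination can be considered as too toxic", with a stated probability of 92% at a true DLT rate of 75%. The other is "If the actual rate is 40% or less, the probability of 14 or fewer DLTs is 82" per cent. No probability of suspension is given at any rate.

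The synopsis repeats the 23-of-30 sentence without the percentages. It follows a different suspension table there (5 of 5, 10 of 12, 23 of 29), and the synopsis design text ties suspension to a DLT rate above 75%.

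**The concern.** The decision rules apply to cohorts that have already passed up to 26 looks (after patients 5 to 30). Such cohorts are a selected set with limited DLT counts, so a fixed 30-patient binomial does not describe them. If the final toxicity threshold lies above any count the monitoring lets through, it can never inform a decision. If suspension is likely at the rate the plan itself assumes, the committee and the sites should know that before accrual starts. And because the synopsis and Section 8.3 print different boundaries, a reader cannot tell which design the stated properties belong to.

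**Working it through.** **Inputs.** From Section 8.3: 30 patients per cohort; prior Beta(1.5, 1.5); looks after each patient from the 5th; suspension when the posterior probability of a DLT rate above 60% is at least 50%; the printed rows of Table 8.2. From the synopsis: its suspension table.

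**Step 1. The plan's own figures, without monitoring.**
- P(X ≤ 14 | n = 30, p = 0.40) = 0.825. The stated 82% reproduces.
- P(X ≥ 23 | n = 30, p = 0.75) = 0.514. The stated 92% does not. Neighbouring thresholds do not give it either: 19 or more is 0.949, and 20 or more is 0.894.

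**Step 2. The boundaries.** After x DLTs in n patients the posterior is Beta(1.5 + x, 1.5 + n − x).
- 6 of 9: Beta(7.5, 4.5), P(p > 0.60) = 0.589, trigger. 5 of 9: Beta(6.5, 5.5), 0.350, no trigger.
- 16 of 26: Beta(17.5, 11.5), 0.526, trigger. 15 of 26: Beta(16.5, 12.5), 0.375, no trigger.

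This rule reproduces every printed row of Table 8.2. It gives 7 for n = 10–11, and 17, 18, 18 and 19 for n = 27 to 30, where no rows are printed. With 75% in place of 60%, the same rule reproduces every row of the synopsis table.

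**Step 3. The largest count a completing cohort can have.**
- Table 8.2, printed rows: at most 15 at n = 26, and 15 + 4 = 19 at n = 30.
- Table 8.2, extended: at most 17 at n = 29, and 17 + 1 = 18 at n = 30.
- Synopsis table: at most 22 at n = 29, and 22 + 1 = 23 at n = 30.

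**Step 4. Exact recursion.** Let f(n, x) be the probability of being unsuspended with x DLTs after n patients. Then f(n, x) = (1 − p) f(n − 1, x) + p f(n − 1, x − 1). Any x at or above the boundary is moved to the suspended total. Monitoring is per cohort, with no restart.

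Table 8.2, extended to n = 30:

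| True DLT rate | Suspended | Complete and ≤ 14 | ≤ 14 given completion | Complete and ≥ 23 |
|---|---|---|---|---|
| 30% | 8% | 91% | 99% | 0 |
| 40% | 23% | 70% (0.695) | 90% (0.903) | 0 |
| 50% | 49% | 33% | 65% | 0 |
| 60% | 78% | 7% | 32% | 0 |
| 75% | 99% | 0.1% | 5% | 0 |

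With the printed rows only, suspension is 8/22/47/77/99%, and the 40% row gives 0.699 joint and 0.901 conditional. If one extended boundary is run on the pooled 60 patients, suspension at 50% is 51%.

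Synopsis table:

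| True DLT rate | Suspended | Complete and ≤ 14 | ≤ 14 given completion | Complete and ≥ 23 |
|---|---|---|---|---|
| 40% | 2.5% | 81.5% | 84% | below 0.01% |
| 50% | 8.6% | 42% | 46% | 0.03% |
| 75% | 70% | 0.1% | 0.3% | 2.5% |

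**The case against.** Four points can be made for the plan.

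- **The 82% is correct arithmetic.** It is, for a fixed sample of 30. A reader might infer that the true figure is simply 70%. The section does not support that: it introduces these rules for cohorts that complete, and on that conditional reading the figure is 90%, which is more favourable than stated. What stands is that 82% is neither the joint nor the conditional probability under Table 8.2.
- **Suspension is not termination.** This stands as a limit on the claim. A trigger leads to committee review, and if accrual resumed, 23 of 30 could occur. A reader might infer that the rule is dead in all circumstances, or that half of cohorts would be closed; neither follows. But the documents give no rule for resuming, and the paragraph is confined to cohorts not stopped for toxicity.
- **Table 8.2 is not the only suspension table.** This is the strongest objection. Under the synopsis table, 23 of 30 is attainable, the joint probability at 40% is close to the stated 82%, and suspension at 50% is far from half. The findings on the 23-of-30 rule, the 82% and the suspension risk are therefore specific to Table 8.2. The synopsis table does not rescue the paragraph, though: the 23-of-30 rule is almost inert there too, with a 2.5% chance of being met at a true 75% rate.
- **No suspension probability is misstated, because none is given.** True. The gap is one of omission, under a heading that promises operating characteristics.

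**Conclusion.** The point holds in this form. The Phase II operating characteristics in Section 8.3 do not belong to the design as monitored. Under Table 8.2 the 23-of-30 rule has probability zero at every true rate, the 82% becomes 70% (joint) or 90% (conditional), and suspension at the assumed 50% rate is 47–49%. These values assume monitoring per cohort, no restart after a trigger, and the 60% criterion read as the posterior probability of a rate above 60%; that reading reproduces all printed rows. Filling the missing rows changes little.

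Under the synopsis table the corresponding figures are 2.5% for 23 or more at a true 75% rate, 81.5% joint at 40%, and 8.6% suspended at 50%. Suspension risk at 50% therefore differs more than fivefold between the tables (47.5 / 8.6 = 5.5). The documents do not settle which table governs, and this review does not choose.

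The 92% is wrong under any reading considered: it is 51% with no monitoring, 2.5% with the synopsis table and zero with Table 8.2.

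**What to change.** 1. Reconcile the synopsis suspension table with Table 8.2, and complete the rows of the adopted table through the last patient monitored.
2. Replace the operating-characteristics text in both the synopsis and Section 8.3 with values computed under the adopted table. For each value, say whether it is joint with completion or conditional on it. State whether monitoring is per cohort or pooled, and that no restart after suspension is assumed.
3. Report the probability of suspension by true DLT rate, including the assumed 50%.
4. Correct the 92%.
5. Remove the 23-of-30 sentence, or restate it for counts that can occur under the adopted table. As an illustration under Table 8.2, 15 to 18 DLTs of 30 have exact one-sided 90% upper bounds of 63% to 72%.

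The cost is wording and a short calculation. The recalculation does not change conduct. The choice between the two tables is the sponsor's, and the existing conflict already requires it.
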